Any Grade	General Guidance	
 Consider consulting an endocrinologist for endocrine events. Consider, as necessary, discussing with study physician. Monitor patients for signs and symptoms of endocrinopathies. Non-specific symptoms include headache, fatigue, behavior changes, changed mental status, vertigo, abdominal pain, unusual bowel habits, polydipsia, polyuria, hypotension, and weakness. Patients should be thoroughly evaluated to rule out any alternative etiology (e.g., disease progression including brain metastases, or infections). Depending on the suspected endocrinopathy, monitor and evaluate thyroid function tests: TSH, free T3 and free T4 and other relevant endocrine and related labs (e.g., blood glucose and ketone levels, HgA1c). For modest asymptomatic elevations in serum amylase and lipase, corticosteroid treatment is not indicated as long as there are no other signs or symptoms of pancreatic inflammation. If a patient experiences an AE that is thought to be possibly of autoimmune nature (e.g., thyroiditis, pancreatitis, hypophysitis, or diabetes insipidus), the investigator should send a blood sample for appropriate autoimmune antibody testing.
-----------	------------------	---

Grade 1	No dose modifications.	
 Monitor patient with appropriate endocrine function tests. For suspected hypophysitis/hypopituitarism, consider consultation of an endocrinologist to guide assessment of early-morning ACTH, cortisol, TSH and free T4; also consider gonadotropins, sex hormones, and prolactin levels, as well as
---------	------------------------	---

Severity (CTCAE v 5.0)	Dose Modifications	Toxicity Management
Grade 2 Including those with symptomatic endocrinopathy	
 – For Grade 2 endocrinopathy other than hypothyroidism and Type 1 diabetes mellitus, hold study drug/study regimen dose until patient is clinically stable. – If toxicity worsens, then treat as Grade 3 or Grade 4. – Study drug/study regimen can be resumed once event stabilizes and after completion of steroid taper. – Patients with endocrinopathies who may require prolonged or continued steroid replacement (e.g., adrenal insufficiency) can be retreated with study drug/study regimen on the following conditions: 
 1. The event stabilizes and is controlled. 2. The patient is clinically stable as per investigator or treating physician's clinical judgement. 3. Doses of prednisone are ≤ 10 mg/day or equivalent. 	
cosyntropin stimulation test (though it may not be useful in diagnosing early secondary adrenal insufficiency).
 
 – If $\text{TSH} < 0.5 \times \text{LLN}$, or $\text{TSH} > 2 \times \text{ULN}$, or consistently out of range in 2 subsequent measurements, include free T4 at subsequent cycles as clinically indicated and consider consultation of an endocrinologist. – Consult endocrinologist to guide evaluation of endocrine function and, as indicated by suspected endocrinopathy and as clinically indicated, consider pituitary scan. – For all patients with abnormal endocrine work up, except those with isolated hypothyroidism or Type 1 DM, and as guided by an endocrinologist, consider short term- corticosteroids (e.g., 1 to 2 mg/kg/day methylprednisolone or IV equivalent) and prompt initiation of treatment with relevant hormone replacement (e.g., hydrocortisone, sex hormones). – Isolated hypothyroidism may be treated with replacement therapy, without study drug/study regimen interruption, and without corticosteroids. – Isolated Type 1 diabetes mellitus (DM) may be treated with appropriate diabetic therapy, without study drug/study regimen interruption, and without corticosteroids. – Once patients on steroids are improving, gradually taper immunosuppressive steroids (as appropriate and with guidance of endocrinologist) over ≥ 28 days and consider prophylactic antibiotics, antifungals, and anti-PJP treatment (refer to current NCCN guidelines for treatment of cancer-related infections [Category 2B recommendation]).^a – For patients with normal endocrine workup (laboratory assessment or MRI scans), repeat laboratory assessments/MRI as clinically indicated.
Grade 3 or 4	
 – For Grade 3 or 4 endocrinopathy other than hypothyroidism and Type 1 diabetes mellitus, hold study drug/study regimen dose until endocrinopathy symptom(s) are controlled. – Study drug/study regimen can be resumed once event stabilizes and after completion of steroid taper. – Patients with endocrinopathies who may require prolonged or continued steroid replacement (e.g., adrenal insufficiency) can be retreated with study drug/study regimen on the following conditions: 
 1. The event stabilizes and is controlled. 2. The patient is clinically stable as per investigator or treating physician's clinical judgement. 3. Doses of prednisone are ≤ 10 mg/day or equivalent. 	
 – Consult endocrinologist to guide evaluation of endocrine function and, as indicated by suspected endocrinopathy and as clinically indicated, consider pituitary scan. Hospitalization recommended. – For all patients with abnormal endocrine work up, except those with isolated hypothyroidism or Type 1 DM, and as guided by an endocrinologist, promptly initiate empiric IV methylprednisolone 1 to 2 mg/kg/day or equivalent, as well as relevant hormone replacement (e.g., hydrocortisone, sex hormones). – For adrenal crisis, severe dehydration, hypotension, or shock, immediately initiate IV corticosteroids with mineralocorticoid activity. – Isolated hypothyroidism may be treated with replacement therapy, without study drug/study regimen interruption, and without corticosteroids. – Isolated Type 1 diabetes mellitus may be treated with appropriate diabetic therapy, without study drug/study regimen interruption, and without corticosteroids. 
Once patients on steroids are improving, gradually taper immunosuppressive steroids (as appropriate and with guidance of endocrinologist) over ≥ 28 days and consider prophylactic antibiotics, antifungals, and anti-PJP treatment (refer to current NCCN guidelines for treatment of cancer-related infections [Category 2B recommendation]).^a

Severity (CTCAE v 5.0)	Dose Modifications	Toxicity Management
Neurotoxicity		
(to include but not be limited to limbic encephalitis and autonomic neuropathy, excluding Myasthenia Gravis and Guillain-Barre)		
Any Grade (depending on the type of neurotoxicity, refer to NCI CTCAE v5.0 for defining the CTC grade/severity)	General Guidance	
 Patients should be evaluated to rule out any alternative etiology (e.g., disease progression, infections, metabolic syndromes, or medications). Monitor patient for general symptoms (headache, nausea, vertigo, behavior change, or weakness). Consider appropriate diagnostic testing (e.g., electromyogram and nerve conduction investigations). Perform symptomatic treatment with neurological consult as appropriate.
Grade 1	No dose modifications.	
 See “Any Grade” recommendations above. Treat mild signs/symptoms as Grade 1 (e.g. loss of deep tendon reflexes or paresthesia)
Grade 2	
 For acute motor neuropathies or neurotoxicity, hold study drug/study regimen dose until resolution to Grade ≤ 1. For sensory neuropathy/neuropathic pain, consider holding study drug/study regimen dose until resolution to Grade ≤ 1. If toxicity worsens, then treat as Grade 3 or 4. Study drug/study regimen can be resumed once event improves to Grade ≤ 1 and after completion of steroid taper. 	
 Consider, as necessary, discussing with the study physician. Obtain neurology consult. Sensory neuropathy/neuropathic pain may be managed by appropriate medications (e.g., gabapentin or duloxetine). Promptly start systemic steroids prednisone 1 to 2 mg/kg/day PO or IV equivalent. If no improvement within 3 to 5 days despite 1 to 2 mg/kg/day prednisone PO or IV equivalent, consider additional workup and promptly treat with additional immunosuppressive therapy (e.g., IV IG).
Grade 3 or 4	
For Grade 3:
 
 Hold study drug/study regimen dose until resolution to Grade ≤ 1. Permanently discontinue study drug/study regimen if Grade 3 imAE does not resolve to Grade ≤ 1 within 30 days. 
For Grade 4:
 
 Permanently discontinue study drug/study regimen. 	
 Consider, as necessary, discussing with study physician. Obtain neurology consult. Consider hospitalization. Promptly initiate empiric IV methylprednisolone 1 to 2 mg/kg/day or equivalent. If no improvement within 3 to 5 days despite IV corticosteroids, consider additional workup and promptly treat with additional immunosuppressants (e.g., IV IG). Once stable, gradually taper steroids over ≥ 28 days.
Peripheral neuromotor syndromes (such as Guillain-Barre and myasthenia gravis)		
Any Grade	General Guidance	
 The prompt diagnosis of immune-mediated peripheral neuromotor syndromes is important, since certain patients may unpredictably experience acute decompensations that can result in substantial morbidity or in the worst case, death. Special care should be taken for certain sentinel symptoms that may predict a more

Severity (CTCAE v 5.0)	Dose Modifications	Toxicity Management
Grade 1	No dose modifications.	
severe outcome, such as prominent dysphagia, rapidly progressive weakness, and signs of respiratory insufficiency or autonomic instability.
 
 – Patients should be evaluated to rule out any alternative etiology (e.g., disease progression, infections, metabolic syndromes or medications). It should be noted that the diagnosis of immune-mediated peripheral neuromotor syndromes can be particularly challenging in patients with underlying cancer, due to the multiple potential confounding effects of cancer (and its treatments) throughout the neuraxis. Given the importance of prompt and accurate diagnosis, it is essential to have a low threshold to obtain a neurological consult. – Neurophysiologic diagnostic testing (e.g., electromyogram and nerve conduction investigations, and “repetitive stimulation” if myasthenia is suspected) are routinely indicated upon suspicion of such conditions and may be best facilitated by means of a neurology consultation. – It is important to consider that the use of steroids as the primary treatment of Guillain-Barre is not typically considered effective. Patients requiring treatment should be started with IV IG and followed by plasmapheresis if not responsive to IV IG. – Consider, as necessary, discussing with the study physician. – Care should be taken to monitor patients for sentinel symptoms of a potential decompensation as described above. – Obtain a neurology consult.
Grade 2	
 – Hold study drug/study regimen dose until resolution to Grade ≤ 1. – Permanently discontinue study drug/study regimen if it does not resolve to Grade ≤ 1 within 30 days or if there are signs of respiratory insufficiency or autonomic instability. 	
 – Consider, as necessary, discussing with the study physician. – Care should be taken to monitor patients for sentinel symptoms of a potential decompensation as described above. – Obtain a neurology consult – Sensory neuropathy/neuropathic pain may be managed by appropriate medications (e.g., gabapentin or duloxetine).

MYASTHENIA GRAVIS:

- Steroids may be successfully used to treat myasthenia gravis. It is important to consider that steroid therapy (especially with high doses) may result in transient worsening of myasthenia and should typically be administered in a monitored setting under supervision of a consulting neurologist.
- Patients unable to tolerate steroids may be candidates for treatment with plasmapheresis or IV IG. Such decisions are best made in consultation with a neurologist, taking into account the unique needs of each patient.
- If myasthenia gravis-like neurotoxicity is present, consider starting AChE inhibitor therapy in addition to steroids. Such therapy, if successful, can also serve to reinforce the diagnosis.

GUILLAIN-BARRE:

- It is important to consider here that the use of steroids as the primary treatment of Guillain-Barre is not typically considered effective.

Severity (CTCAE v 5.0)	Dose Modifications	Toxicity Management
Grade 3 or 4	
For Grade 3:
 
 Hold study drug/study regimen dose until resolution to Grade ≤ 1. Permanently discontinue study drug/study regimen if Grade 3 imAE does not resolve to Grade ≤ 1 within 30 days or if there are signs of respiratory insufficiency or autonomic instability. 
For Grade 4:
 
Permanently discontinue study drug/study regimen.
	
 Patients requiring treatment should be started with IV IG and followed by plasmapheresis if not responsive to IV IG. Consider, as necessary, discussing with study physician. Recommend hospitalization. Monitor symptoms and obtain neurological consult. 
MYASTHENIA GRAVIS:
 
 Steroids may be successfully used to treat myasthenia gravis. They should typically be administered in a monitored setting under supervision of a consulting neurologist. Patients unable to tolerate steroids may be candidates for treatment with plasmapheresis or IV IG. If myasthenia gravis-like neurotoxicity present, consider starting AChE inhibitor therapy in addition to steroids. Such therapy, if successful, can also serve to reinforce the diagnosis. 
GUILLAIN-BARRE:
 
 It is important to consider here that the use of steroids as the primary treatment of Guillain-Barre is not typically considered effective. Patients requiring treatment should be started with IV IG and followed by plasmapheresis if not responsive to IV IG.
Myocarditis		
Any Grade	
General Guidance
 
Discontinue drug permanently if biopsy-proven immune-mediated myocarditis.
	
 The prompt diagnosis of immune-mediated myocarditis is important, particularly in patients with baseline cardiopulmonary disease and reduced cardiac function. Consider, as necessary, discussing with the study physician. Monitor patients for signs and symptoms of myocarditis (new onset or worsening chest pain, arrhythmia, shortness of breath, peripheral edema). As some symptoms can overlap with lung toxicities, simultaneously evaluate for and rule out pulmonary toxicity as well as other causes (e.g., pulmonary embolism, congestive heart failure, malignant pericardial effusion). A Cardiology consultation should be obtained early, with prompt assessment of whether and when to complete a cardiac biopsy, including any other diagnostic procedures. Initial work-up should include clinical evaluation, BNP, cardiac enzymes, ECG, echocardiogram (ECHO), monitoring of oxygenation via pulse oximetry (resting and exertion), and additional laboratory work-up as indicated. Spiral CT or cardiac MRI can complement ECHO to assess wall motion abnormalities when needed. Patients should be thoroughly evaluated to rule out any alternative etiology (e.g., disease progression, other medications, or infections)
Grade 1 (asymptomatic or mild symptoms*; clinical or diagnostic observations only; intervention not indicated)	
No dose modifications required unless clinical suspicion is high, in which case hold study drug/study regimen dose during diagnostic work-up for other etiologies. If study
	
 Monitor and closely follow up in 2 to 4 days for clinical symptoms, BNP, cardiac enzymes, ECG, ECHO, pulse oximetry (resting and exertion), and laboratory work-up as clinically indicated. Consider using steroids if clinical suspicion is high.

Severity (CTCAE v 5.0)	Dose Modifications	Toxicity Management
*Treat myocarditis with mild symptoms as Grade 2.	drug/study regimen is held, resume after complete resolution to Grade 0.	
Grade 2, 3 or 4 (Grade 2: Symptoms with moderate activity or exertion) (Grade 3: Severe with symptoms at rest or with minimal activity or exertion; intervention indicated; new onset of symptoms*) (Grade 4: Life-threatening consequences; urgent intervention indicated (e.g., continuous IV therapy or mechanical hemodynamic support))	
 If Grade 2 -- Hold study drug/study regimen dose until resolution to Grade 0. If toxicity rapidly improves to Grade 0, then the decision to reinitiate study drug/study regimen will be based upon treating physician's clinical judgment and after completion of steroid taper. If toxicity does not rapidly improve, permanently discontinue study drug/study regimen. If Grade 3-4, permanently discontinue study drug/study regimen. 	
 Monitor symptoms daily, hospitalize. Promptly start IV methylprednisolone 2 to 4 mg/kg/day or equivalent after Cardiology consultation has determined whether and when to complete diagnostic procedures including a cardiac biopsy. Supportive care (e.g., oxygen). If no improvement within 3 to 5 days despite IV methylprednisolone at 2 to 4 mg/kg/day, promptly start immunosuppressive therapy such as TNF inhibitors (e.g., infliximab at 5 mg/kg every 2 weeks). Caution: It is important to rule out sepsis and refer to infliximab label for general guidance before using infliximab. Once the patient is improving, gradually taper steroids over ≥ 28 days and consider prophylactic antibiotics, antifungals, or anti-PJP treatment (refer to current NCCN guidelines for treatment of cancer-related infections [Category 2B recommendation]).^a
* Consider "new onset of symptoms" as referring to patients with prior episode of myocarditis.		

Myositis/Polymyositis ("Poly/myositis")

Any Grade	General Guidance	
 Monitor patients for signs and symptoms of poly/myositis. Typically, muscle weakness/pain occurs in proximal muscles including upper arms, thighs, shoulders, hips, neck and back, but rarely affects the extremities including hands and fingers; also difficulty breathing and/or trouble swallowing can occur and progress rapidly. Increased general feelings of tiredness and fatigue may occur, and there can be new-onset falling, difficulty getting up from a fall, and trouble climbing stairs, standing up from a seated position, and/or reaching up. If poly/myositis is suspected, a Neurology consultation should be obtained early, with prompt guidance on diagnostic procedures. Myocarditis may co-occur with poly/myositis; refer to guidance under Myocarditis. Given breathing complications, refer to guidance under Pneumonitis/ILD. Given possibility of an existent (but previously unknown) autoimmune disorder, consider Rheumatology consultation. Consider, as necessary, discussing with the study physician. Initial work-up should include clinical evaluation, creatine kinase, aldolase, LDH, BUN/creatinine, erythrocyte sedimentation rate or C-reactive protein level, urine myoglobin, and additional laboratory work-up as indicated, including a number of possible rheumatological/antibody tests (i.e., consider whether a rheumatologist consultation is indicated and could guide need for rheumatoid factor, antinuclear antibody, anti-smooth muscle, antisynthetase [such as anti-Jo-1], and/or signal-recognition particle antibodies). Confirmatory testing may include electromyography, nerve conduction studies, MRI of the muscles, and/or a muscle biopsy. Consider Barium swallow for evaluation of dysphagia or dysphonia.
-----------	------------------	--

Severity (CTCAE v 5.0)	Dose Modifications	Toxicity Management
Grade 1 (mild pain)	No dose modifications.	
 Patients should be thoroughly evaluated to rule out any alternative etiology (e.g., disease progression, other medications, or infections).
Grade 2 (moderate pain associated with weakness; pain limiting instrumental activities of daily living [ADLs])	
 Hold study drug/study regimen dose until resolution to Grade ≤ 1. Permanently discontinue study drug/study regimen if it does not resolve to Grade ≤ 1 within 30 days or if there are signs of respiratory insufficiency. 	
 Monitor and closely follow up in 2 to 4 days for clinical symptoms and initiate evaluation as clinically indicated. Consider Neurology consult. Consider, as necessary, discussing with the study physician. Monitor symptoms daily and consider hospitalization. Obtain Neurology consult, and initiate evaluation. Consider, as necessary, discussing with the study physician. If clinical course is rapidly progressive (particularly if difficulty breathing and/or trouble swallowing), promptly start IV methylprednisolone 2 to 4 mg/kg/day systemic steroids along with receiving input from Neurology consultant If clinical course is not rapidly progressive, start systemic steroids (e.g., prednisone 1 to 2 mg/kg/day PO or IV equivalent); if no improvement within 3 to 5 days, continue additional work up and start treatment with IV methylprednisolone 2 to 4 mg/kg/day If after start of IV methylprednisolone at 2 to 4 mg/kg/day there is no improvement within 3 to 5 days, consider start of immunosuppressive therapy such as TNF inhibitors (e.g., infliximab at 5 mg/kg every 2 weeks). Caution: It is important to rule out sepsis and refer to infliximab label for general guidance before using infliximab. Once the patient is improving, gradually taper steroids over ≥ 28 days and consider prophylactic antibiotics, antifungals, or anti-PJP treatment (refer to current NCCN guidelines for treatment of cancer-related infections [Category 2B recommendation]).^a
Grade 3 or 4 (Grade 3: pain associated with severe weakness; limiting self-care ADLs)	
For Grade 3:
 
 Hold study drug/study regimen dose until resolution to Grade ≤ 1. Permanently discontinue study drug/study regimen if Grade 3 imAE does not resolve to Grade ≤ 1 within 30 days or if there are signs of respiratory insufficiency. 	
 Monitor symptoms closely; recommend hospitalization. Obtain Neurology consult, and complete full evaluation. Consider, as necessary, discussing with the study physician. Promptly start IV methylprednisolone 2 to 4 mg/kg/day systemic steroids along with receiving input from Neurology consultant.
Grade 4: life-threatening consequences; urgent intervention indicated	
For Grade 4:
 
 Permanently discontinue study drug/study regimen. 	
 If after start of IV methylprednisolone at 2 to 4 mg/kg/day there is no improvement within 3 to 5 days, consider start of immunosuppressive therapy such as TNF inhibitors (e.g., infliximab at 5 mg/kg every 2 weeks). Caution: It is important to rule out sepsis and refer to infliximab label for general guidance before using infliximab. Consider whether patient may require IV IG, plasmapheresis. Once the patient is improving, gradually taper steroids over ≥ 28 days and consider prophylactic antibiotics, antifungals, or anti-PJP treatment (refer to current NCCN guidelines for treatment of cancer-related infections [Category 2B recommendation]).^a

^aASCO Educational Book 2015 “Managing Immune Checkpoint Blocking Antibody Side Effects” by Michael Postow MD.

^bFDA Liver Guidance Document 2009 Guidance for Industry: Drug Induced Liver Injury – Premarketing Clinical Evaluation.

AChE Acetylcholine esterase; ADL Activities of daily living; AE Adverse event; ALP Alkaline phosphatase test; ALT Alanine aminotransferase; AST Aspartate aminotransferase; BUN Blood urea nitrogen; CT Computed tomography; CTCAE Common Terminology Criteria for Adverse Events; ILD Interstitial lung disease; imAE immune-mediated adverse event; IG Immunoglobulin; IV Intravenous; GI Gastrointestinal; LFT Liver function tests; LLN Lower limit of normal; MRI Magnetic resonance imaging; NCI National Cancer Institute; NCCN National Comprehensive Cancer Network; PJP *Pneumocystis jirovecii* pneumonia (formerly known as *Pneumocystis carinii* pneumonia); PO By mouth; T3 Triiodothyronine; T4 Thyroxine; TB Total bilirubin; TNF Tumor necrosis factor; TSH Thyroid-stimulating hormone; ULN Upper limit of normal.

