7.4.2 Definitions of Dose Limiting Toxicities (DLT)

A DLT will be defined as any Grade 3 or higher treatment-related toxicity that occurs during the DLT observation phase (8 weeks post Y90-RE), including:

- Any event resulting in a delay of cycle 2 by \geq 14 calendar days
- Any Grade 4 immune related adverse event (irAE)
- Any Grade 3 immune related AE (irAE) that does not resolve to \leq Grade 1 or to baseline with immunosuppressive therapy within 3 weeks
- Any Grade 3 colitis
- Any Grade 3 noninfectious pneumonitis irrespective of duration
- Grade 4 neutrophil count decreased lasting longer than 5 calendar days
- Grade 4 platelet count decreased
- Grade 3 platelet count decreased with hemorrhage
- Any \geq Grade 2 pneumonitis that does not resolve to \leq Grade 1 within 7 days of the initiation of maximal supportive care
- Any other Grade 3 irAE (excluding colitis or pneumonitis), that does not downgrade to Grade 2 within 7 days after onset of the event despite optimal medical management including systemic corticosteroids or does not downgrade to \leq Grade 1 or baseline within 14 days
- Liver transaminase elevation $> 8 \times$ ULN
- Total bilirubin $> 5 \times$ ULN
- AST or ALT $> 5-8 \times$ ULN with concurrent increase in total bilirubin $> 2 \times$ ULN without evidence of cholestasis or alternative explanations, e.g., viral hepatitis, disease progression in the liver, etc. (Hyll's Law). Exception: If it is present at cycle 3 but resolves at cycle 4 it is not a DLT.
- Any \geq grade 3 non-hematologic toxicity, except:
 - Grade 3 nausea or vomiting that lasts < 48 hours and resolves to \leq Grade 1 either spontaneously or with conventional medical intervention
 - Grade 3 nausea, vomiting, and diarrhea lasting < 72 hours in the absence of maximal medical therapy
 - Grade 4 vomiting and diarrhea lasting < 72 hours in the absence of maximal medical therapy
 - Grade 3 hypertension in the absence of maximal medical therapy
 - Grade 3 metabolic abnormalities (e.g. hypokalemia, hypomagnesemia, hypocalcemia, hypophosphatemia) that recover to \leq Grade 1 within 48 hours
 - \geq Grade 3 electrolyte abnormality lasting < 72 hours, is not clinically complicated, and resolves spontaneously or responds to conventional medical intervention.
 - Grade 3 or 4 elevation in serum amylase and/or lipase that are not associated with clinical or radiographic evidence of pancreatitis.
 - Grade 3 rash < 5 calendar days

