Grade 2 AST, ALT, or TBIL AST or ALT $> 3.0 - 5 \times \text{ULN}$ and/or TBIL $> 1.5 - 3 \times \text{ULN}$	
 Hold study drug/study regimen dose until resolution to AST or ALT $\leq 3.0 \times \text{ULN}$ and/or TB $\leq 1.5 \times \text{ULN}$. If toxicity worsens, then treat as described for elevations in the row below. If toxicity improves to AST or ALT $\leq 3.0 \times \text{ULN}$ and/or TB $\leq 1.5 \times \text{ULN}$, or baseline, resume study drug/study regimen after completion of steroid taper. 	
 Regular and frequent checking of LFTs (e.g., every 1 to 2 days) until elevations of these are improving or resolved. If no resolution to AST or ALT $\leq 3.0 \times \text{ULN}$ and/or TB $\leq 1.5 \times \text{ULN}$ in 1 to 2 days, consider, as necessary, discussing with study physician. If event is persistent (> 3 to 5 days) or worsens, promptly start prednisone 1 to 2 mg/kg/day PO or IV equivalent. If still no improvement within 3 to 5 days despite 1 to 2 mg/kg/day of prednisone PO or IV equivalent, consider additional work up and start prompt treatment with IV methylprednisolone 2 to 4 mg/kg/day. If still no improvement within 3 to 5 days despite 2 to 4 mg/kg/day of IV methylprednisolone, promptly start immunosuppressives (i.e., mycophenolate mofetil).^a Disyycess with study physician if mycophenolate mofetil is not available. Infliximab should NOT be used. Once the patient is improving, gradually taper steroids over ≥ 28 days and consider prophylactic antibiotics, antifungals, and anti-PJP treatment (refer to current NCCN guidelines for treatment of cancer-related infections [Category 2B recommendation]).^a
AST or ALT $> 5.0 \times \text{ULN}$ and/or	For elevations in transaminases $\leq 8 \times \text{ULN}$ or elevations in TBIL $\leq 5 \times \text{ULN}$:	
 Promptly initiate empiric IV methylprednisolone at 1 to 4 mg/kg/day or equivalent. If still no improvement within 3 to 5 days despite 1 to 4 mg/kg/day methylprednisolone IV or equivalent, promptly start treatment with

Severity (CTCAE v 5.0)	Dose Modifications	Toxicity Management

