TBIL $>3.0 \times$ ULN	
 Hold study drug/study regimen dose until resolution to AST or ALT $\leq 3.0 \times$ ULN and/or TB $\leq 1.5 \times$ ULN, or baseline Resume study drug/study regimen if elevations downgrade to AST or ALT $\leq 3.0 \times$ ULN and/or TB $\leq 1.5 \times$ ULN, or baseline within 14 days and after completion of steroid taper. Permanently discontinue study drug/study regimen if the elevations do not downgrade to AST or ALT $\leq 3.0 \times$ ULN and/or TB $\leq 1.5 \times$ ULN or baseline within 14 days. 
For elevations in transaminases $>8 \times$ ULN or elevations in bilirubin $>5 \times$ ULN, permanently discontinue study drug/study regimen.
 
Permanently discontinue study drug/study regimen for any case meeting Hy's law criteria (AST and/or ALT $>3 \times$ ULN + bilirubin $>2 \times$ ULN without initial findings of cholestasis (i.e., elevated alkaline phosphatase) and in the absence of any alternative cause.^b Note that this does not apply to the week 2 (cycle 3) post Y90-RE when this is usually seen and subsides in the upcoming weeks (cycle 4). Also for those with Gilbert's syndrome, would need to rely on AST/ALT rather than total bilirubin.
	
 immunosuppressive therapy (i.e., mycophenolate mofetil). Discuss with study physician if mycophenolate is not available. Infliximab should NOT be used. Perform hepatology consult, abdominal workup, and imaging as appropriate. Once the patient is improving, gradually taper steroids over ≥ 28 days and consider prophylactic antibiotics, antifungals, and anti-PJP treatment (refer to current NCCN guidelines for treatment of cancer-related infections [Category 2B recommendation]).^a

Nephritis or renal dysfunction (elevated serum creatinine)

Any Grade	General Guidance	
		
 Consult with nephrologist. Monitor for signs and symptoms that may be related to changes in renal function (e.g., routine urinalysis, elevated serum BUN and creatinine, decreased creatinine clearance, electrolyte imbalance, decrease in urine output, or proteinuria). Patients should be thoroughly evaluated to rule out any alternative etiology (e.g., disease progression or infections). Steroids should be considered in the absence of clear alternative etiology even for low-grade events (Grade 2), in order to prevent potential progression to higher grade event.

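### Appendix VII liver row: hold and permanent stop overlap when both tests are raised and one passes its stop limit, and the and/or release can be met while a raised test is still high

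*Combined protocol and SAP*

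**What the plan says.** The hepatitis (elevated LFTs) part of Appendix VII has a row entered at "AST or ALT $> 5.0 \times \text{ULN}$ and/or" bilirubin above 3.0 × ULN. Its dose-modification column contains these rules:

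- **Hold:** transaminases up to 8 × ULN "or elevations in TBIL" up to 5 × ULN.
- **Permanent stop:** "For elevations in transaminases $>8 \times$ ULN or elevations in bilirubin $>5 \times$ ULN, permanently discontinue study drug/study regimen".
- **End of hold:** "until resolution to AST or ALT $\leq 3.0 \times$ ULN and/or TB $\leq 1.5 \times$ ULN, or baseline". Resumption uses the same pair of limits joined in the same way. So does the 14-day permanent stop, in the negative.
- **Extra condition for resuming:** "or baseline within 14 days and after completion of steroid taper". The same row says to "gradually taper steroids over ≥ 28 days" once the patient is improving.
- **Hy's law line:** permanent stop for AST and/or ALT above 3 × ULN with bilirubin above 2 × ULN, without cholestasis or another cause, and not applied at week 2 after Y90-RE.

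The opening row of the liver table treats an elevation as any value above ULN. The Grade 2 row repeats the *and/or* release limits but has no permanent-stop threshold.

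Table 8.21 (Section 8.2) works by grade. Grade 2 AST, ALT or bilirubin increases are held, with permanent discontinuation if not back to Grade 0-1 in 2 weeks. Grade 3-4 increases are permanently discontinued. Section 8.0 makes that table strict for the first two cycles and a guideline afterwards.

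**The concern.** A hold and a permanent stop should exclude each other, and a hold should end only when the tests that caused it have recovered. Here *or* joins the limits in both the hold and the stop, and *and/or* joins them in the release. Two investigators with the same laboratory results can therefore reach opposite actions, each with support in the text.

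Section 1.4.5 expects liver enzymes to rise in most patients in the first one to two weeks after Y90-RE. Y90-RE is given with cycle 2, so these events arise largely once Table 8.21 is no longer strict. Dose levels 2 to 4 differ in the number of durvalumab doses after Y90-RE (one, two and three). If the liver rules are applied differently from patient to patient, the treatment actually delivered at a level, and the tolerability seen there, depends partly on how a connector was read.

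**Working it through.** The plan states no figure on this point, so the check is one of logic. Let T be a transaminase and B bilirubin, both in multiples of ULN, with all limits taken from the Appendix VII row.

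- Entry: T > 5 or B > 3
- Hold: T ≤ 8 or B ≤ 5
- Stop: T > 8 or B > 5
- Release, *or* branch: T ≤ 3 or B ≤ 1.5
- Release, *and* branch: T ≤ 3 and B ≤ 1.5

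**Step 1, hold against stop.** The complement of (T > 8 or B > 5) is (T ≤ 8 and B ≤ 5). The printed hold uses *or*, so the two sets overlap whenever one test is above its stop limit and the other is not.

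| Results (× ULN) | Hold | Stop | Release, *or* | Release, *and* |
|---|---|---|---|---|
| AST 10, B 1.2 | yes | yes | met | not met |
| AST 10, B 2 | yes | yes | not met | not met |
| B 6, AST 2 | yes | yes | met | not met |
| AST 10, B 0.8 | only on bare numbers | yes | met | not met |
| AST 6, B 0.8 | yes | no | met | not met |
| AST 6, B 4 | yes | no | not met | not met |
| AST 10, B 6 | no | yes | not met | not met |

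The first three rows collide even if an elevation must exceed ULN. The Hy's law line does not settle them: B is not above 2 in the first two, and AST is not above 3 in the third.

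A grid in steps of 0.1 (T to 20, B to 10) gives 200 × 100 − 50 × 30 = 18,500 points inside the row. The overlap is 120 × 50 + 80 × 50 = 10,000 points on bare numbers. It is 120 × 40 + 70 × 50 = 8,300 if the second test must be above ULN. With *and* in the hold, the overlap is 0 and no point is left uncovered. These counts describe the rule and are not patient frequencies.

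**Step 2, release when several tests are raised.**

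- Start: AST 6, B 1.8. The row is entered (6 > 5), the hold applies (6 ≤ 8), the stop does not, and Hy's law does not (1.8 ≤ 2). Release is not met on either branch (6 > 3 and 1.8 > 1.5).
- Later: AST 6, B 1.4. The *or* branch is met (1.4 ≤ 1.5), so the 14-day stop does not apply. The *and* branch is not met (6 > 3), so at day 14 the stop applies.
- Start: AST 7, ALT 4, with ALT later at 2.9 and AST still 7. The condition names AST *or* ALT, so it is met by ALT alone.

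**Step 3, against Table 8.21.** Appendix VII ends Grade 2 at 5 × ULN for transaminases and 3 × ULN for bilirubin, so the row examined here lies above Grade 2. Table 8.21 permanently discontinues Grade 3-4 increases. Appendix VII allows a hold and resumption for part of the same range.

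**The case against.** The best defence is that the text can be read sensibly. The verbs are about resolving and downgrading, and a value that was never raised can do neither. The *and/or* in the release also mirrors the row's entry condition, which suggests that it means whichever test triggered the row. This has force for a rise in one test only. It does not help when two tests were raised and one has recovered, because an elevation has then come down to a listed limit.

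Three stronger readings are tempting, and the documents do not support them.

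- A reader might infer that any isolated rise meets hold and stop together. Isolated rises above 5 to 8 × ULN (transaminases) or above 3 to 5 × ULN (bilirubin) meet the hold only. Above those limits, with the other test normal, the overlap exists only if the words about elevations are ignored.
- A reader might infer that a patient is simply declared resolved and re-dosed. Resuming also requires a completed steroid taper, set at 28 days or more in this row. A hold starting at week 2 could then not end before week 6 (2 + 28/7), the last scheduled dose. The protection is weaker in the Grade 2 row, where Appendix VII starts steroids only if the event persists or worsens.
- A reader might infer that DLT counts change. Section 7.4.2 lists "Liver transaminase elevation" above 8 × ULN and total bilirubin above 5 × ULN as separate items, without these connectors.

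The adverse reaction rates in the appended device insert cannot size the problem either. The all-grade figures come from hepatocellular carcinoma studies and do not show who would reach a hold.

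Table 8.21 might be thought to settle the matter. It is strict for two cycles only, and it conflicts with Appendix VII.

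**Conclusion.** The point stands as a defect in a stated safety rule: for some sets of results it directs two incompatible actions and gives no order of precedence. The hold/stop collision is certain when one test is above its stop limit and the other is raised but within its own limit. The Hy's law line resolves part of that region, but not results such as AST 10 with bilirubin 1.2 × ULN. The release defect is certain when only one of several raised tests has recovered. Read literally, a test that was never raised can also satisfy the release, but the verbs in the text point away from that reading.

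The Grade 2 row has the release defect only. No sample size, error rate or DLT definition is touched, and the number of patients affected cannot be estimated from the documents. The conclusion rests on the connectors as printed and on the table's own sense of elevation as a value above ULN. The sponsor should correct it.

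**What to change.** Reconcile the hold, release, resumption and stop conditions in the two liver rows of Appendix VII so that every set of results falls under exactly one action. State release test by test, for every test that met the hold condition, so that recovery of one test cannot stand in for another. Then reconcile the rows with Table 8.21 for Grade 3-4 AST, ALT and bilirubin increases, and say which text governs after cycle 2. In the same edit, say what the 14 days limit, since a taper of at least 28 days cannot finish within them.

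The repair of the logic costs a few words in two table rows and needs no change of threshold. The reconciliation with Table 8.21 needs a clinical decision. The thresholds and the choice of rule stay with the sponsor.
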